#### **4.2.3 Notification of Sponsor of Serious Adverse Events**

**Within 24 hours of identifying an SAE, regardless of the presumed relationship to the investigational product, the investigator or qualified designee must complete the SAE Report form and fax to MedImmune Patient Safety.**

MedImmune contact information:

Patient Safety

MedImmune

MedImmune, as sponsor of the study being conducted under an Investigational New Drug Application (IND), is responsible for reporting certain SAEs as IND safety reports to the US Food and Drug Administration (FDA), other applicable regulatory authorities, and participating investigators, in accordance with the USA Code of Federal Regulations (21 CFR Parts 312.32 and 312.33) ICH Guidelines, and/or local regulatory requirements. MedImmune may be required to report certain SAEs to regulatory authorities within 7 calendar days of being notified about the event; therefore, it is important that investigators submit additional information requested by MedImmune as soon as it becomes available.

Investigators should provide all available information at the time of form completion. Investigators should not wait to collect additional information to fully document the event before notifying MedImmune of an SAE. When additional information becomes available, submit a follow-up SAE report form with the new information. Any follow-up information to an SAE also needs to be provided to MedImmune Patient Safety within 24 hours of learning of the new information.

#### **4.2.4 Notification of Institutional Review Board or Independent Ethics Committee of Serious Adverse Events**

The investigator must comply with the applicable regulatory requirements related to the reporting of SAEs to the IRB or IEC. The IRB or IEC must be informed in a timely manner by the principal investigator of serious AEs occurring at their site during the study. Investigators must also submit safety information provided by MedImmune to the IRB or IEC as detailed in Section [7.2](#).

#### 4.2.5 Recording of Serious Adverse Events

Serious adverse events will be recorded on the SAE REPORT FORM using a recognized medical term or diagnosis that accurately reflects the event. Each SAE will be assessed by the investigator for severity, relationship to the investigational product, and possible etiologies. See Section 4.2.1 for the definition of SAEs, and Section 4.3 and Section 4.4 regarding guidelines for assessment of severity and relationship, respectively.

For the purposes of study analysis, if the event has not resolved at the end of the study reporting period, it will be documented as ongoing. For purposes of regulatory safety monitoring, the investigator is required to follow the event to resolution and report to the sponsor the outcome of the event using the SAE REPORT FORM.

#### 4.3 Assessment of Severity

Assessment of severity is one of the responsibilities of the investigator in the evaluation of AEs and SAEs. The determination of severity should be made by a health care professional who is qualified to review AE information, provide a medical evaluation of AEs, and classify AEs based upon medical judgment and the severity categories of *Grade 1*, *Grade 2*, *Grade 3*, *Grade 4*, or *Grade 5* using the NCI CTCAE v3.0.

Adverse events not described within the NCI CTCAE v3.0 will be reported using the severity categories as follows:

Grade 1:	Mild AE
Grade 2:	Moderate AE
Grade 3:	Severe AE
Grade 4:	Life-threatening or disabling AE
Grade 5:	Death related to AE

It is important to distinguish between serious and severe AEs. Severity is a measure of intensity whereas seriousness is defined by the criteria in Section 4.2.1. An AE of severe intensity need not necessarily be considered serious. For example, nausea that persists for several hours may be considered severe nausea, but not an SAE. On the other hand, a stroke that results in only a limited degree of disability may be considered a mild stroke, but would be an SAE.

#### 4.4 Assessment of Relationship

An AE is considered “product-related” for the purposes of regulatory reporting if the investigator, the medical monitor, or the Patient Safety physician assesses the AE as possibly, probably, or definitely related to investigational product. This is not a conclusive determination of causal association between the product and the event.

Whenever the investigator’s assessment is unknown or unclear, the AE is treated as product-related for the purposes of reporting to regulatory authorities. An AE may be deemed to be not related to the product for purposes of regulatory reporting only if the investigator, medical monitor, and Patient Safety physician, if applicable, agree that the AE is not product-related.

The investigator is required to provide an assessment of relationship of AEs and SAEs to the investigational product. A number of factors should be considered in making this assessment including: 1) the temporal relationship of the event to the administration of investigational product; 2) whether an alternative etiology has been identified; and 3) biological plausibility. The following guidelines should be used by investigators to assess the relationship of an AE to investigational product administration.

##### Relationship assessments that indicate an “Unlikely Relationship” to investigational product:

*None:* The event is related to an etiology other than the investigational product (the alternative etiology must be documented in the study subject’s medical record).

*Remote:* The event is unlikely to be related to the investigational product and likely to be related to factors other than investigational product.

##### Relationship assessments that indicate a “Likely Relationship” to investigational product:

*Possible:* There is an association between the event and the administration of the investigational product, and there is a plausible mechanism for the event to be related to investigational product; but there may also be alternative etiology, such as characteristics of the subject’s clinical status or underlying disease.

*Probable:* There is an association between the event and the administration of investigational product, a plausible mechanism for the event to be related to the investigational product, and the event could not be reasonably explained by known characteristics of the subject's clinical status or an alternative etiology is not apparent.

*Definite:* There is an association between the event and the administration of investigational product, a plausible mechanism for the event to be related to the investigational product, and causes other than the investigational product have been ruled out and/or the event re-appeared on re-exposure to the investigational product.

For AEs that occur prior to the administration of investigational product, an assessment of protocol relatedness must be made. Protocol-related AEs may occur as a result of procedures required during the screening process (eg, blood collection, washout of an existing medication) prior to the initial administration of investigational product. For AEs that occur before administration of investigational product, only those that are assessed by the investigator as protocol-related should be reported to the sponsor. The following guidelines should be used by investigators to assess the relationship of an AE to a protocol-required procedure:

**Protocol related:** The event occurred due to a procedure/intervention that was described in the protocol for which there is no alternative etiology present in the subject's medical record.

**Not protocol related:** The event is related to an etiology other than the study procedure (the alternative etiology must be documented in the study subject's medical record).

#### **4.5 Other Events Requiring Immediate Reporting**

The following events must be reported ***within 24 hours*** by fax to MedImmune Patient Safety using the fax notification form:

- 1) Any withdrawal of consent during the study
- 2) Pregnancy or intent to become pregnant\*

\* Subjects who become pregnant during the study period must not receive additional doses of investigational product but will be followed for the duration of the study. A pregnancy should be followed for outcome, any premature terminations reported, and the health status of the mother and child, including date of delivery and the child's gender and weight, should be reported to MedImmune Patient Safety after delivery.

#### **4.6 Safety Management During the Study**

The MedImmune medical monitor has primary responsibility for the ongoing medical review of safety data throughout the study. This includes immediate review of SAEs and timely review of other AEs reported during the study. The MedImmune Patient Safety Specialist has responsibility for the day-to-day safety monitoring of the study, including the receipt, review, investigation, and follow-up of SAEs reported by the clinical study sites.

The Safety Monitoring Committee (SMC) will independently review cumulative safety surveillance data, as well as the decisions of the medical monitor regarding dose escalation, on a regular basis throughout the study and make recommendations regarding further conduct of the study. The SMC will also review safety data at other time points in response to AEs felt to be medically significant by the medical monitor. The SMC is composed of at least 2 MedImmune physicians who are not directly involved in the day-to-day operations of the study, and at least 2 physicians who are not employees of MedImmune.

#### **4.7 Interruption or Discontinuation of Study Dosing in Individual Subjects**

An individual subject will not receive any further investigational product if any of the following occur in the subject in question:

- 1) Withdrawal of consent
- 2) Allergic reactions  $\geq$  Grade 2. Infusion reactions  $\leq$  Grade 3 that respond to medical therapy or slowing the infusion rate and that are of limited duration will not necessitate dose interruption or discontinuation. Any infusion or allergic reaction that necessitates the use of systemic pressor agents will cause dose discontinuation in that subject.
- 3) Pregnancy or intent to become pregnant
- 4) DLT (see Section 4.10 for definition of DLTs)
- 5) Recurrence of Grade 3 or Grade 4 hematologic or non-hematologic toxicity after the first cycle of treatment
- 6)  $\geq$  Grade 2 toxicities (after completion of Cycle 1) that do not return to  $\leq$  Grade 1 or baseline within 7 days unless clearly attributable to another cause such as disease progression or an accident
- 7) Grade  $\geq$  2 toxicities that cause a cumulative delay of  $\geq$  21 days in 3 consecutive cycles
- 8) Documentation of disease progression

- 9) Event which, in the opinion of the investigator, contraindicates further dosing such as intercurrent illnesses, significant drug toxicities or complications if judged by the investigator to be in the best interest of the subject
- 10) Subject non-compliance.
- 11) Treatment with another investigational agent
- 12) Initiation of alternative anticancer therapy

Subjects who are permanently discontinued from investigational product will be followed for the full study period (through 30 days after the last dose of MEDI-575), including the collection of any protocol-specified blood and skin specimens, unless consent is withdrawn.

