#### **3.5.5 Dose Modifications and Toxicity Management**

Dose modifications of MEDI-575 will be based on hematologic and nonhematologic toxicities that cannot be attributed to another cause, such as disease progression or accident, following the first cycle of treatment ([Table 3.5.5-1](#)). Both hematologic and nonhematologic

toxicities will be graded according to NCI CTCAE V3.0. All DLTs must be documented as an AE on the source document. If enrolled in the weekly schedule, a cycle will be considered complete after administration of 3 doses for all cycles after the first cycle. If enrolled in the every 3-week schedule, a cycle will be considered complete after the administration of 1 dose.

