**Table 3.5.5-1                   MEDI-575 Dose Modification Table**

Hematologic or Nonhematologic Toxicity	Dose Modification of MEDI-575
≤ Grade 1	None
Grade 2	
Withhold MEDI-575 for up to 7 days until resolution to ≤ Grade 1 or baseline and resume at current dose level. Grade 2 laboratory toxicities that do not have clinical significance may not require dose delay. The Medical Monitor should be consulted in the event of Grade 2 laboratory toxicities that are deemed clinically insignificant to determine if dosing may continue.
 
Discontinue MEDI-575 if MEDI-575 is withheld for > 7 days without resolution of toxicity to ≤ Grade 1 or baseline unless clearly attributable to another cause such as disease progression or accident.

Grade 3 or 4	
First Occurrence:
 
Withhold MEDI-575 for up to 7 days until resolution to ≤ Grade 1 or baseline. Discontinue MEDI-575 if no clinical benefit has been documented.
 
For subjects who experience Grade 3 or Grade 4 toxicity that resolves as above, and who have achieved some degree of clinical benefit while on MEDI-575 therapy, the United States Food and Drug Administration (FDA) will be consulted regarding the possibility of continued administration of MEDI-575. MEDI-575 therapy should not be continued without agreement from the FDA.
 
Discontinue MEDI-575 if MEDI-575 is withheld for > 7 days without resolution of toxicity to ≤ Grade 1 or baseline regardless of clinical benefit.
 
Second Occurrence:
 
Discontinue MEDI-575.

If toxicity ≥ Grade 3 that is at least possibly attributable to MEDI-575 is observed in a subject or subjects during the second or subsequent treatment cycle, dose escalation will be temporarily suspended to review the cumulative safety data. Such an event may prompt cessation of dose escalation or modification of the dose escalation scheme, including a decrease of subsequent doses from the first cycle dose, if appropriate. Subjects may continue to receive MEDI-575 during this review and subjects may continue to be enrolled into an open cohort until a determination of necessary action, if any, is made.

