#### **4.10 Definitions of Dose-limiting Toxicities**

Dose-limiting toxicities will be graded according to the NCI CTCAE V3.0. The DLT period for Dose Cohort 1 only will begin with the single lead-in administration of MEDI-575 at the dose level of 0.5 mg/kg (Cycle 1, Study Day 1) and continue through the entire first cycle of treatment (Cycle 1, Study Day 28) for a total of 28 days. The DLT period for Dose Cohorts 2

through 7 will begin with the administration of the first dose of MEDI-575 and continue through the entire first cycle of treatment (Cycle 1, Study Day 1 through Cycle 1, Study Day 21).

A DLT is defined as:

- 1) Any Grade 3 or higher non-hematologic toxicity that occurs during the DLT assessment period where a cause other than the investigational product (such as disease progression or accident) cannot be reasonably justified with the following exceptions:
  - Grade 3 fever (in the absence of neutropenia) defined as  $> 40.0^{\circ}\text{C}$  ( $>104.0^{\circ}\text{F}$ ) that resolves to normal or baseline within 24 hours of treatment and is not considered an SAE; or
  - Grade 3 rigors/chills that respond to optimal therapy.
- 2) Any Grade 3 or higher hematologic toxicity where a cause other than the investigational product (such as disease progression or accident) cannot be reasonably justified.

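### Section 4.7 Item 2 lets dosing continue after a brief, responsive Grade 3 infusion reaction, against Table 3.5.5-1 after Cycle 1 and against Item 4 with Section 4.10 in Cycle 1

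*Protocol*

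**What the plan says.** Protocol Section 4.7 lists events after which a subject "will not receive any further investigational product if any of the following occur". Item 2 of that list deals with allergic and infusion reactions. It ends dosing for allergic reactions of Grade 2 or higher and for any reaction needing systemic pressors. Between those two rules it says that infusion reactions of Grade 3 or lower "that respond to medical therapy or slowing the infusion rate and that are of limited duration will not necessitate dose interruption or discontinuation".

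The other rules that reach the same event are:

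- **Section 4.7 Item 4** ends dosing for any DLT and states no exception.
- **Section 4.10 Item 1** defines the non-hematologic DLT as "Any Grade 3 or higher non-hematologic toxicity that occurs during the DLT assessment period" for which no cause other than the drug can reasonably be justified. It has two exceptions. One is a Grade 3 fever that resolves quickly, without neutropenia, and is not an SAE. The other is "Grade 3 rigors/chills that respond to optimal therapy". Infusion reactions as such are not excepted.
- **Section 4.7 Item 5** ends dosing on "Recurrence of Grade 3 or Grade 4 hematologic or non-hematologic toxicity after the first cycle of treatment".
- **Section 3.5.5 and Table 3.5.5-1** apply to toxicities that cannot be put down to another cause "such as disease progression or accident, following the first cycle of treatment". At a first Grade 3 or 4 toxicity the table withholds drug, then instructs: "Discontinue MEDI-575 if no clinical benefit has been documented". A subject with benefit may continue only with FDA agreement. A second occurrence ends dosing.

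Section 3.5.4 allows prophylaxis before later doses in subjects who have had an infusion reaction, with no limit on grade.

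**The concern.** An investigator whose subject has a short Grade 3 infusion reaction that settles with treatment will look first at the item written for infusion reactions. That item says dosing need be neither interrupted nor stopped, and Section 3.5.4 reads as though later doses are expected. Elsewhere the protocol takes the same subject off drug, or holds drug until the FDA agrees. No sentence says which instruction governs.

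At stake is whether an individual subject is redosed in a first-in-human antibody study. The question concerns dosing still to come: Cohorts 6 and 7 receive the largest doses per infusion, and Section 2.4 lengthens their infusion because of the greater protein load.

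**Working it through.** **The test event.** Take a Grade 3 infusion reaction with no other cause, which responds to treatment or a slower rate, is brief, needs no pressors, and is not merely the fever or rigors/chills that Section 4.10 exempts. Apply each rule as written.

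| Situation | Section 4.7 Item 2 | Other rules |
|---|---|---|
| Cycle 1 | Continue | DLT under Section 4.10 Item 1, so Item 4 stops drug. Table 3.5.5-1 does not yet apply. |
| After Cycle 1, first occurrence | Continue, no interruption | Table 3.5.5-1 withholds drug, then stops it unless there is documented benefit and FDA agreement. Item 5 is not triggered. |
| After Cycle 1, second occurrence | Continue; no limit on repeats stated | Item 5 and Table 3.5.5-1 both stop drug. |

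The clearest conflict is in the second row. Item 2 says no interruption is needed, while the table requires one and then a decision outside the investigator's hands. A brief reaction may well have resolved before the next scheduled dose, so withholding alone might cost no dose. The benefit condition and the FDA step still decide whether the next dose is given.

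The discontinuation conflict is confined to Grade 3. At Grade 2 the table withholds until resolution and resumes at the same dose, so a reaction that settles promptly does not end treatment.

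**How many subjects are under the rule at the larger doses.** First, the plan's own figure in Section 5.2: 7 cohorts × 3 = 21 and 7 cohorts × 6 = 42 evaluable subjects, as stated. With the same cohort sizes from Table 3.5.2-1 and the 6 every-3-week expansion subjects from Section 2.4:

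- Minimum: 2 cohorts × 3 + 6 = 12.
- Maximum: 2 cohorts × 6 + 6 = 18.

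So 12 to 18 planned subjects would receive 25 or 35 mg/kg. The 6 weekly expansion subjects, and any subject from Cohorts 1 to 5 still on drug, are under the same wording, but at no more than 15 mg/kg (Section 4.9 Item 6).

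**Effect on escalation.** Section 4.10 counts the Cycle 1 event as a DLT whether or not the subject is redosed. The change in DLT count is 0, so escalation decisions and sample size do not move.

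**The case against.** The best defence concerns Cycle 1. Each item in Section 4.7 is a separate trigger and any one is enough. The disputed sentence sits inside Item 2, so it can be read as limiting only that item: a responsive infusion reaction is not by itself a stop as an allergic reaction, and Item 4 still stops a DLT. On this reading the Grade 3 wording keeps some work to do, because Section 4.10 exempts certain Grade 3 fevers and responsive rigors/chills, and there the two sections agree. This softens the Cycle 1 conflict and probably reflects the intent. It does not remove the conflict, because the sentence is unqualified and speaks of dosing in general. Nor does it reconcile the sentence with the table after Cycle 1, where withholding is mandatory and there is no exception for infusion reactions or rigors.

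There are also safeguards. Item 2 stops any reaction needing pressors, and Item 9 lets the investigator stop drug. Section 4.8 halts dosing and entry after any anaphylactic reaction. Section 3.5.5 suspends escalation for review after possibly related toxicity of Grade 3 or higher in later cycles. These limit the harm. None says which rule governs redosing.

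Four stronger readings are tempting and are not supported:

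- A reader might infer that DLT counting or escalation is compromised. It is not, because Section 4.10 already counts the event.
- A reader might infer that Item 5 stops a first reaction. It requires a recurrence after Cycle 1.
- A reader might count Cycle 1 doses at risk in Cohorts 1 to 5. Section 2.4 reports no DLTs in those cohorts, so such figures are largely historical.
- A reader might put all 12 expansion subjects among those on the larger infusions. Six of them are on the weekly schedule.

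**Conclusion.** The point holds as a contradiction in a subject-level safety rule. It is firm after Cycle 1, against Table 3.5.5-1. It is weaker in Cycle 1, where the any-item lead-in favours Item 4 but the text of Item 2 points the other way. It concerns Grade 3 infusion reactions that are attributable to the drug, brief and responsive; in Cycle 1 it covers only those outside the Section 4.10 exceptions.

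The count of 12 to 18 subjects at 25 or 35 mg/kg assumes that Cohorts 6 and 7 both open at 3 to 6 subjects and that the every-3-week expansion fills with 6. It is the number under the rule, not the number expected to react, since the protocol gives no infusion-reaction rate. With no effect on DLT counts, escalation or sample size, the severity is minor to should-fix.

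**What to change.** Add one clause to the infusion-reaction sentence in Section 4.7 Item 2: *unless the reaction is a DLT (Section 4.10), or Item 5 or Table 3.5.5-1 requires that dosing be withheld or discontinued*. The clause must cover withholding as well as stopping; otherwise a subject with clinical benefit who is waiting for FDA agreement would still face an instruction that no interruption is needed.

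Capping the sentence at Grade 2 would be simpler. However, it would also remove Item 2's permission for the Grade 3 fever and rigors/chills that Section 4.10 deliberately exempts, so the added clause is preferable.

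The cost is one phrase by amendment, with no change to the DLT definition, escalation rule, sample size or analysis. The downside is that a few subjects with responsive Grade 3 reactions will have drug withheld or stopped. After Cycle 1 that includes rigors/chills, for which the table has no exception.

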### **3.6 Schedule of Evaluations**

All subjects who are assigned a SID and receive any investigational product will be followed according to the protocol regardless of the number of doses received, unless consent for follow-up is withdrawn. The investigator must notify the sponsor or designee of deviations from protocol visits or evaluations and, if applicable, these evaluations must be rescheduled or performed at the nearest possible time to the original schedule. Protocol deviations will be recorded on the source document with an explanation for the deviation. The investigator must comply with the applicable requirements related to the reporting of protocol deviations to the Institutional Review Board (IRB)/ Independent Ethics Committee (IEC).

Subjects/legal representatives will be instructed to call study personnel to report any abnormalities during the intervals between study visits and to come to the study site if medical evaluation is needed and the urgency of the situation permits. For emergency and other unscheduled visits to a medical facility other than the study site, medical records will be obtained by the investigator and made available to the sponsor or designee during monitoring visits.

A schedule of screening and on-study visit procedures is presented in [Table 3.6-1](#) and [Table 3.6-2](#), and a schedule of follow-up visit procedures is presented in [Table 3.6-3](#), followed by a detailed description of each visit. All visits during Cycle 2 and subsequent visits may occur in a  $\pm$  2-day window to accommodate schedule changes, but doses of MEDI-575 must not occur more frequently than every 6 days if in the weekly schedule or every 19 days if in the every 3-week schedule.

For Cohorts 6 and 7, and subjects enrolled in the every 3-week schedule of the dose-expansion phase, visits and study procedures on Study Days 8 and 15 are required only

during the first cycle. For Cycle 2 and subsequent cycles, no Study Day 8 or Study Day 15 visits are required.

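### Section 4.7 Item 6 requires permanent discontinuation for a persistent, clinically insignificant Grade 2 laboratory toxicity that Table 3.5.5-1 allows to be dosed through, and Item 6 does not say when its 7 days start

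*Protocol*

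**What the plan says.** Section 4.7 is mandatory. Its opening line reads: "An individual subject will not receive any further investigational product if any of the following occur in the subject in question". Item 6 in that list covers Grade 2 and higher: "Grade 2 toxicities (after completion of Cycle 1) that do not return to" Grade 1 or lower, "or baseline within 7 days unless clearly attributable to another cause such as disease progression or an accident". It makes no distinction between laboratory and clinical toxicity, or by clinical significance.

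Table 3.5.5-1, which Section 3.5.5 applies to toxicity after the first cycle, gives three instructions for Grade 2:
- General rule: "Withhold MEDI-575 for up to 7 days until resolution to ≤ Grade 1 or baseline and resume at current dose level".
- Laboratory exception: "Grade 2 laboratory toxicities that do not have clinical significance may not require dose delay". The Medical Monitor is consulted on whether dosing may go on. No time limit is given.
- Stop: discontinue if drug is withheld for more than 7 "days without resolution of toxicity to ≤ Grade 1 or baseline unless clearly attributable to another cause such as disease progression or accident".

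Section 3.5.2 sends the reader to Section 4.7 for withdrawal and to Section 3.5.5 for delays. It does not rank them. For the every 3-week schedule, Section 3.6 adds: "For Cycle 2 and subsequent cycles, no Study Day 8 or Study Day 15 visits are required".

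**The concern.** Both passages govern the same subjects in the same period, and both decide whether a subject stays on drug. If they part company, a site following the table keeps a subject whom a site following Section 4.7 removes for good. Continuing under the table could also be recorded as a deviation from Section 4.7. Safety and tolerability are a primary objective, so discontinuations for toxicity should mean the same thing at every site.

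There are two possible points of divergence. One is scope: the table has a laboratory exception and Item 6 has none. The other is the clock: the table counts days that drug is withheld, while Item 6 attaches its 7 days to the toxicity and names no starting point. The clock would matter most where doses are 21 days apart, because a toxicity can then begin and end between doses.

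**Working it through.** The plan states no figure to reproduce. The check sets the two rules side by side for Grade 2 toxicity after Cycle 1.

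| Case | Table 3.5.5-1 | Section 4.7 Item 6 | Result |
|---|---|---|---|
| a. Clinical or clinically significant toxicity present at a due dose, resolved within 7 days | Hold, then resume | Not triggered | Agree |
| b. As (a), but drug withheld more than 7 days and unresolved | Discontinue | Discontinue | Agree |
| c. Clearly due to another cause | No stop | No stop | Agree |
| d. Clinically insignificant laboratory toxicity, more than 7 days, no other cause | Dosing may continue after Medical Monitor consultation | Permanent stop | Contradict |
| e. Toxicity longer than 7 days that resolves before the next due dose or within the permitted hold | No stop | Stop if the 7 days run from onset; no stop if they run from the withheld dose | Depends on reading |

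Case (d), weekly schedule. A Grade 2 laboratory value above baseline is found at Cycle 2 Day 1 and judged insignificant, and the subject is dosed. Laboratory tests are scheduled again on Days 8 and 15. If the value is unchanged on Day 15, it has lasted 15 − 1 = 14 days, which exceeds 7. Under the table the Day 15 dose may be given; under Item 6 the subject may receive no further drug. The start of the clock does not matter here. If Item 6 is counted from onset or first detection, it is triggered. If it is counted only from a withheld dose, it is never triggered, because no dose was withheld; but Item 6 as written does not mention withholding.

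Case (e), every 3-week schedule, onset reading:
- Onset Day 3, resolved Day 12: 12 − 3 = 9 days, more than 7.
- Next dose due: Day 1 + 21 = Day 22, so 0 days are withheld.
- The table asks for nothing; Item 6 would end treatment.

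Case (e), weekly schedule, onset reading:
- Onset Day 9. The Day 15 dose may be held up to 7 days, to Day 22.
- Duration tolerated by the table: 22 − 9 = 13 days.
- Item 6 limit: Day 9 + 7 = Day 16. The difference is 13 − 7 = 6 days.

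Who could be exposed. Only subjects who reach Cycle 2 and then have such an event are affected. Planned enrolment on the every 3-week schedule is 2 × 3 + 6 = 12 to 2 × 6 + 6 = 18, which is the pool and not the number affected. The protocol gives no rate for reaching Cycle 2 or for Grade 2 events.

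**The case against.** The strongest reply is that the two passages are one rule written twice. They share the 7 days, the standard of resolution, the period after Cycle 1 and the exception for another cause. That is right for cases (a) to (c). A reader might infer that the passages give opposite instructions for Grade 2 toxicity in general; the documents do not support this.

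The reply also has force on the clock. Appendix 2 explains the Item 6 wording about completion of Cycle 1 as clarifying when a dosing delay is allowed, so the sponsor seems to regard Item 6 as a dose-delay rule. Item 7 points the same way. On the every 3-week schedule, with one dose per cycle and at most 7 days of delay, a cumulative 21 days over three cycles needs 3 × 7, a full hold each time. Under an onset clock that could happen only if every toxicity began on the day the dose was due. Against this, Item 7 speaks of delay in so many words and Item 6 does not. The clock conflict therefore stands only as an unstated start point, not as a proven contradiction.

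On observability, Section 3.6 asks subjects to report problems between visits, and Section 3.7.1 asks for prompt repeat of abnormal laboratory results. These partly offset the missing mid-cycle visits.

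Finally, one can say that the table is the more specific text, that its purpose is explained in Appendix 2, and that the Medical Monitor oversees its use across only about 3 to 6 sites. This makes divergent practice less likely, but it does not remove the conflict: Section 4.7 is worded as an absolute bar and the protocol states no order of precedence.

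**Conclusion.** The point holds in a narrow form. There is one plain contradiction, case (d), and one ambiguity, the unstated start of Item 6's 7 days. The contradiction rests on the literal text of Item 6. The worked examples for case (e) rest on the further assumption that its clock runs from onset, which the protocol neither states nor excludes.

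The consequence is inconsistent permanent discontinuation of individual subjects after Cycle 1, and inconsistent reporting of it. Its frequency cannot be estimated from the protocol.

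Two larger consequences might be inferred and are not supported. DLT and MTD determination is not affected, because the DLT period is Cycle 1 and both rules start after it. A bias in the weekly versus every 3-week comparison, or in the choice for expansion, is not shown. It would require the onset reading, no size can be put on it, safety is summarised descriptively, and both schedules are expanded by design with about 6 subjects each. Safety data do inform the expansion dose, but nothing in the protocol shows that this inconsistency would change it.

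**What to change.** Reconcile Section 4.7 Item 6 with Table 3.5.5-1 so that the rule is stated once and the other place refers to it; for example, Item 6 could cite the table. The reconciled text should do two things:
- treat clinically insignificant Grade 2 laboratory toxicity in the same way in both places, including whether any time limit applies;
- name one start for the 7 days.

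The sponsor should also confirm that the chosen start can be observed with the visits provided on the every 3-week schedule from Cycle 2 on. Which version stands is a clinical decision for the sponsor, and none is proposed here. The cost is about one sentence in a protocol amendment, with no added subjects and no change to the analysis. If the sponsor chooses a start that scheduled visits cannot show, it would also need to say how resolution is to be documented.
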